6.3.2 Sample size

Our sample size estimates are based on previous high and low transmission season surveys conducted during the first ICEMR (2010–2017) in areas similar to the clusters that will be selected for this study. Based on these data, we anticipate that 13%-18% of households will contain a child 7-18 months old. The risk of infection in this age group is estimated to be 21% (30% high and 20% low transmission seasons). In children \leq 10 years of age the risk of infection is estimated to be 31% (46% in the high and 32% in the low transmission seasons). The within-cluster correlation is estimated at 0.004 (0.05 in the high and 0.00 in the low transmission seasons) and 0.14 (0.22 in the high and 0.06 in the low transmission seasons) for children aged 7-18 months and \leq 10 years of age, respectively. Based on these data, by studying the 25 clusters with 20 households with a child 7-18 months per intervention arm, we will analyze 500 children aged 7-18 months and a similar or larger number of older children. For power calculations, we assumed that these proportions represented the risk of incident cases of infection.

This proposed sample size will allow us to estimate moderate effectiveness of the combined interventions (versus no intervention) with 80% power in 2-sided tests, accounting for within-cluster correlation, and with α -level of 0.05. For instance, based on the cross-sectional estimations of individual risk of malaria infection obtained at enrollment of each cohort, we will be able to

detect the effectiveness of 34% (36% and 33% when stratifying by season) in children 7-18 month-old (Hayes, 2009). In a repeated measure analysis, with within-subject correlation of 1.5 to 2 times larger than within-cluster correlation, we will be able to detect effectiveness of 34-37% in children 7-18 month old (Liu, 2002).

For entomological assessments, 100 households from each of the two arms will be visited for entomological analysis including *Anopheles* abundance, female mosquito parity, and source of blood meal and sporozoite prevalence. Based on our previous experience, we have found an average of one *Anopheles* mosquito per household sampled (although with very heterogeneous distribution), and 75-95% human-biting prevalence.

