6.5 Analysis Plan

To describe the study population, evaluate potential confounding, and identify sources of selection bias, baseline information will be summarized and compared across children who do/do not comply with either RTS,S vaccination, or with PBO nets, or with both. These analyses will be primarily conducted at an individual level, but to assess robustness of results, comparisons will also be conducted at cluster levels. Analysis at individual levels will be performed using random-effect models to account for the within subject correlation. Linear, logistic, and over-dispersed Poisson models will be used to analyze continuous, categorical, and count variables, respectively. Baseline information will also be assessed for children ≤10 years old at individual- and household-level through nested random effects accounting for correlation of subjects within households.

For analysis of effectiveness on prevalence and transmission, separate models will be fitted to estimate total and direct effectiveness (Hayes, 2009; Hallaron, 2010) in children aged 7-18 months at six time points. Analysis will be primarily done at the individual level, with intervention

groups compared through nested random effect models (accounting for correlation across time). A subgroup analysis will include children who will have been vaccinated within 3 months from Month (M) 1. Models will be logistic for the occurrence of infection and presence of gametocytes, and overdispersed Poisson or zero-inflated for gametocyte density. In all analysis, the linearity of association of the outcome with predictors will be evaluated through semiparametric regression and, if necessary, predictors will be categorized or transformed. In secondary analyses, all incident events will be assessed in individual-level analysis through negative binomial models (corresponding to discrete proportional hazard multiple event models) with nested random effects. We will also explore comparisons of the number of new infection events per follow-up month in over-dispersed Poisson models. Since adherence to vaccination (post-randomization variable) can introduce selection bias, we will also explore estimating total and direct effectiveness using causal inference models.

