To examine antibodies of exposure, two approaches will evaluate the association between levels of exposure antibodies and intervention groups: 1) antibody levels will be summarized using partial least square regression (PLS); 2) levels of individual antibodies will be used. Summary scores and antibody levels will be compared over time between the two groups through joint outcome (shared parameter) models (Verbeke, 2010). Moreover, joint outcome models will be fit for positivity of responses and a zero-inflated model will be fit for the breadth of responses (number of antibodies that are positive in a subject).

For analysis of effectiveness in all household members (in Phase 1, children aged >18 months and \leq 10 years old), indirect effectiveness at the individual level at four-time points will be estimated. Also, in nested random effect models for individual analysis, we will account for correlation across visits, within the household. The household-level analysis will be conducted by summarizing outcomes in the household, and also in nested random effect models, using the same link functions described above.

For entomological outcomes, analysis of effectiveness will be performed comparing intervention groups through zero inflated negative binomial models with random effects, including as offsets hours of capture effort or number of captured mosquitoes, as appropriate. Outcome variables will include abundance of *Anopheles*, sporozoite rates, blood-meal originated from humans, and female parity in households.

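### Effectiveness is sized as 1 − risk ratio, but the main infection and gametocyte models give conditional odds ratios and section 6.5 states no conversion between the two

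*Combined protocol and SAP*

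**What the plan says.** Section 6.3.2 plans on proportions infected, which it takes to stand for the risk of an incident infection. For the design "by studying the 25 clusters with 20 households with a child 7-18 months per intervention arm", and "with 80% power in 2-sided tests, accounting for within-cluster correlation", it says the study can "detect the effectiveness of 34% (36% and 33% when stratifying by season) in children 7-18 month-old". A repeated-measures version gives 34-37%. No detectable effectiveness is stated for the older children.

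Section 6.5 estimates total and direct effectiveness in the 7-18 month group by comparing groups in nested random-effect models. For the binary outcomes it says: "Models will be logistic for the occurrence of infection and presence of gametocytes". The household-level analysis of the older children is also done in nested random-effect models, "using the same link functions described above". Negative binomial models for incident events are named as secondary. Over-dispersed Poisson models for new infections per month and causal-inference models are to be explored. No part of 6.5 names a risk ratio, a standardised risk, a log link for the binary outcomes, or 1 − odds ratio.

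**The concern.** A percentage effectiveness has no meaning until its scale is fixed. The sample-size section fixes it implicitly as a proportional reduction in risk. The main analysis model reports something else: the odds ratio for a child or cluster with a given random effect. Two things separate this from the risk ratio. Infection is common here, which pulls the odds ratio further from 1 than the risk ratio. Conditioning on random effects pulls it further still.

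If the analyst takes 1 − odds ratio as effectiveness, the result cannot be set beside the planned 34%, and it will look larger than the reduction in the proportion infected. Phase 1 is meant to estimate impact and to inform a larger study, so the reported size matters.

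**Working it through.** **Inputs (all from 6.3.2).** 500 children aged 7-18 months per arm in 25 clusters of 20; two-sided α 0.05; 80% power. Comparison-arm risk p0 and within-cluster correlation (ICC) at 7-18 months: 21% and 0.004 overall, 30% and 0.05 in the high season, 20% and 0.00 in the low season. For children up to 10 years: 46% and 0.22 in the high season, 32% and 0.06 in the low season. Within-subject correlation is taken there as 1.5 to 2 times the cluster value.

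**Step 1: reproduce the stated figures.** Design effect = 1 + 19 × ICC; effective n = 500 / design effect; p1 = p0(1 − e). Solve for e in

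−ln(1 − e) = (1.960 + 0.842) × √[(1 − p0)/(n·p0) + (1 − p1)/(n·p1)].

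| p0 | ICC | Design effect | Effective n | e, risk-ratio scale | Stated | e, if meant as 1 − OR |
|---|---|---|---|---|---|---|
| 21% | 0.004 | 1.076 | 464.7 | 33.6% | 34% | 38.9% |
| 30% | 0.05 | 1.95 | 256.4 | 36.1% | 36% | 44.3% |
| 20% | 0.00 | 1.00 | 500 | 33.4% | 33% | 38.3% |

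The last column solves the same problem for the log odds ratio. All three stated values match the risk-ratio scale after rounding. A difference-of-proportions formula gives 33.2%, 35.5% and 33.0%, also close, with power at the stated values of 81.9%, 81.2% and 80.0%. Had the stated percentages meant 1 − odds ratio, power would be only about 67%, 59% and 66%. The planned scale is therefore 1 − risk ratio.

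**Step 2: read the same effect as 1 − odds ratio, ignoring random effects.** OR = [p1/(1 − p1)] / [p0/(1 − p0)].

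- p0 = 20%, e = 33%: p1 = 0.134; OR = 0.1547/0.2500 = 0.619; 1 − OR = 38.1%, a gap of 5.1 points.
- p0 = 21%, e = 34%: p1 = 0.1386; OR = 0.1609/0.2658 = 0.605; 39.5%, a gap of 5.5 points.
- p0 = 30%, e = 36%: p1 = 0.192; OR = 0.2376/0.4286 = 0.554; 44.6%, a gap of 8.6 points.
- p0 = 46%, e = 34% (assumed): p1 = 0.3036; OR = 0.4360/0.8519 = 0.512; 48.8%, a gap of 14.8 points.

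**Step 3: allow for the random effects.** One normal random intercept stands for the nested structure. Its standard deviation is chosen so that the variance of the individual risks divided by p0(1 − p0) equals the ICC. The two conditional logits are then solved by numerical integration so that they average to p0 and p1, and the conditional OR is the exponential of their difference.

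| p0 | e | Correlation used | Random-intercept variance | Conditional 1 − OR | Gap, points |
|---|---|---|---|---|---|
| 21% | 34% | 0.004 to 0.008 | 0.02 to 0.05 | 39.6% to 39.7% | 5.6 to 5.7 |
| 30% | 36% | 0.05 to 0.10 | 0.26 to 0.57 | 46.1% to 47.7% | 10.1 to 11.7 |
| 32% | 34% (assumed) | 0.06 | 0.31 | 44.9% | 10.9 |
| 46% | 34% (assumed) | 0.22 | 1.42 | 57.3% | 23.3 |

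The upper correlations in the first two rows are twice the cluster value. At 20% risk the stated ICC is 0, so the step 2 figure stands. If the 0.22 is on the latent logistic scale, the last gap is 20.9 points.

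**Step 4: effect on significance.** With 500 per arm and no clustering, the Wald z for log RR against log OR is 2.94 against 2.96 (21% risk, 34% effect), 3.90 against 3.94 (30%, 36%) and 4.99 against 5.06 (46%, 34%). The test result barely depends on the scale.

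**The case against.** The strongest reply is that the plan never says it will report 1 − odds ratio. A random-effect logistic model can also produce standardised risks, and so a risk ratio. That stands. A reader might infer that the reported effectiveness will be inflated; the documents show only that the conversion is unstated.

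A reader might also infer that logistic regression is the only model for infection. It is not: the negative binomial and Poisson models also concern infection and are not on the odds scale. They are secondary or exploratory and address counts of events, so they do not settle what effectiveness on prevalence means in the main analysis. The causal-inference models are named without an effect measure.

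Two further inferences go too far. One is that the scale would distort the Go/No-Go decision. Table 2 mentions Go/No-Go criteria but gives no effectiveness threshold, and section 6.1 ties the next step to significant results, which step 4 shows are hardly affected. The other is that effectiveness would differ by season and age through baseline risk alone. That presumes a constant risk ratio; with a constant odds ratio the risk ratios would vary instead, and the documents establish neither.

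Finally, it is tempting to quote one range up to 20 points or more. The upper end needs 46% risk, a conditional odds ratio, and an effect size borrowed from the younger group. A random-intercept variance of 1 at 21% risk would imply a correlation of about 0.14, far above the stated 0.004, so it cannot be used for the 7-18 month group.

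**Conclusion.** The point holds as an unspecified effect measure: effectiveness was sized as 1 − risk ratio, the main model's direct output is a conditional odds ratio, and nothing in 6.5 links them.

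The overstatement is conditional on reading the coefficient as 1 − odds ratio. In the group for which the study was sized it is about 5-6 points at 20-21% risk and about 9-12 points at 30% risk, so 36% would read 45% (marginal) or 46-48% (conditional). For children up to 10 years at 46% risk, an assumed 34% reduction would read about 15 points (marginal) to 23 points (conditional) too high.

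These sizes assume that the stated risks apply to the comparison arm, that the stated correlations are on the proportion scale, that one random intercept stands for the nesting, and that the true effect is near the planned size. Away from that size the gap can be smaller: at 20% risk it is 3.8 points for a 20% effect and 3.3 points for an 80% effect. What is at stake is the reported size of effect and its comparability with the planned figure, rather than the significance test.

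**What to change.** In section 6.5, define effectiveness as 1 − risk ratio and name how it is obtained. Either of these would do:

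- Keep the nested logistic model. Standardise predicted risks over the sample under each group, integrating over the random effects, and take the ratio, with a bootstrap or delta-method interval that respects clustering.
- Fit a log-link Poisson model to the binary outcome with cluster-robust standard errors.

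Apply the same rule to gametocyte presence and to the models for older household children. If odds ratios are also shown, label them as such and do not present them as effectiveness.

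The cost is a few sentences in the plan and slightly more analysis work. No design or data change is needed. The effectiveness figure will be less flattering than 1 − odds ratio would have been.

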4. JUSTIFICATION

Despite massive scale-up of malaria control interventions in Malawi, especially ITNs, malaria disease burden still remains high. This study will assess the impact of two new interventions being introduced into the Malawi national malaria control program. The outstanding research question is

a) What is the impact of RSS,S vaccine on *P. falciparum* prevalence and transmission?

The focus of past RTS,S clinical trials has always been the protective efficacy against clinical disease. Given the large-scale cluster-randomized introductions of the vaccines, and the existing ICEMR community-based surveillance infrastructure, we will evaluate the effect of RTS,S vaccination on the prevalence of *P. falciparum* infection in the vaccinated children and their household members and also on various measures of transmission. This critical information has never previously been explored in evaluating malaria vaccine effectiveness. In addition, the use of serological markers will generate measures of transmission for individuals on a finer scale than entomological measures alone and will allow controlling for exposure level in the analysis. Accurate estimations of effectiveness in prior vaccination studies have been hampered by the lack of measures of individual exposure.

[figure not shown]

Figure 1. Mortality of *An. funestus* exposed to seven LLIN types was <40% except to PermaNet 3.0.

b) Does the use of PBO nets decrease exposure to malaria infection and limit transmission? Although PBO nets are likely to have more potent insecticide activity, only one study has been published to date that shows that the implementation of PBO nets decreases human malaria infection (Protopopoff 2018).

c) What are the combined effects of RTS,S vaccine and PBO nets?

While it is possible that the impact of RTS,S vaccine plus the impact of PBO nets is additive, human behavior, parasite dynamics and vector responses may lead to either synergistic or antagonistic effects when they are combined. The factorial study design proposed in this application allows the evaluation of the impact and interaction of these two interventions.

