Findings from this study will have implications for policy makers since understanding both the direct and indirect, population-level benefits of malaria vaccination and PBO nets will be critical when countries decide whether to adopt these intensive interventions. Hence the data obtained in this study will be used to enhance program effectiveness, both at national and international level. This study will be divided into two phases. This protocol is particularly focused on detailing the first phase of the study, although it briefly summarizes the proposal of the second phase of the study.

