6 METHODS

6.1 Study Design

This will be a prospective cohort study. This is a preliminary study to determine if we can detect an impact of RTS,S vaccine combined with PBO nets on parasitological, entomological and/or serological evidence of infection and transmission. If this preliminary study yields significant results, we will have the opportunity to apply for funding from our sponsor (US National Institutes of Health) for a much larger study that will assess the impact of each of these interventions individually and how they interact with each other. If we are approved to conduct this multi-arm study, we will submit a new protocol to COMREC and the MSU IRB for review and approval.

Using malaria and vaccine registers, we will establish community-based cohorts of children age-eligible to receive RTS,S vaccination from the two extreme groups: i.e. Nyambi health centre in Machinga and Kalembo health centre in Balaka. The Machinga district, is undergoing implementation of both RTS,S vaccination and PBO nets (RTS,S and PBO interventions). Balaka households do not receive RTS,S vaccination and only receive conventional nets arms (Table 1). We will enroll children of the age that would be eligible for vaccination and all of the children over nineteen months and under ten years of age in their house. We will conduct interviews and collect specimens at enrolment and at 2, 4 and 6 months, as described below. During these visits, data on individual, household, social, and behavioral determinants, immunization status, ITN use will be collected.

Table 1: Overview of study design and methods

Specific Objective 1: To estimate the impact of PBO nets and RTS,S vaccine on Plasmodium infection prevalence and transmission in Malawi.		
Methods	Data sources	Key variables/ outcome

Phase 1: Recruited from Nyambi Machinga health centre – in catchment areas that receive RTS,S vaccination and PBO nets.
 
Recruited from Kalembo health centre in Balaka – in catchment areas that receive conventional nets and no malaria vaccination.
	
Interviews of parent/guardians participantsBlood samplesCaptured mosquitosHuman reporting about NetsFinger prick blood specimens	
Plasmodium falciparum infectionGametocyte presenceAnopheles spp. abundanceAnopheles gravidityAnopheles sporozoite rateNet usageImmunization statusSerological markers

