6.2 Study location

The study will be carried out in Machinga and Balaka Districts, in Southern Malawi. *Machinga District* (14.55 S, 35.40 E), located ~120 km northeast of Blantyre, is a poor rural district. Malaria transmission is intense and year-round, peaking during the rainy season (November through May). Between July 2013 and June 2014, an estimated 162,500 (1-year risk of 28%) malaria cases were reported and accounted for 24% of the total Outpatient Department (OPD) attendance (the total population of Machinga District is ~572,000 people). In 2015, malaria annual incidence was 367 cases/1,000 individuals. The use of ITNs is widespread in the district; findings from the 2015-2016 MDHS reported that 66.3% of the individuals and 80.5% of under-five children slept under an ITN in the previous night.

Balaka District (15.01° S, 35.01° E), forms a boundary with Machinga and is also a poor, rural district. Malaria is generally high in the district with intense, year-round transmission that also peaks during the rainy season. Between July 2013 and June 2014, malaria cases were accounted for 29% of the total OPD attendance (the total population of Balaka District is ~372,000 people). In 2015, malaria annual incidence was 310 cases/1,000 population. Findings from 2015-2016 MDHS indicated that 67.5% of the population and 87.3% of under-five children slept under an ITN in the previous night.

The timing for this proposal is optimal as we will be able to take advantage of the Malawi government-funded nationwide ITN distribution campaign (2018) and the RTS,S evaluation project (2019). In November 2018, Malawi undertook a country-wide bed net campaign, distributing nets to each household with a target of one net for every two people. In Machinga district, PBO nets were distributed, while neighboring Balaka District conventional pyrethroid-treated bed nets were given. About eight months later, both districts are part of the vaccination of infants and young children with the RTS,S vaccine, where children in selected clusters will receive RTS,S whilst children in some clusters of the same district would act as controls. The Malawi Ministry of Health has asked our ICEMR team, through the College of Medicine Malaria Alert Centre, to support the evaluation of RTS,S vaccination, thus providing a perfect opportunity to assess the combined effects of these interventions.

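### Indirect effectiveness in older household children cannot be estimated from the Nyambi–Kalembo comparison

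*Combined protocol and SAP*

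**What the plan says.** Section 6.5 sets the estimand for the older household children: "indirect effectiveness at the individual level at four-time points will be estimated". It gives no definition, names no comparison other than the two arms, and does not restrict by the child's own net use. For target children aged 7–18 months it plans models for total and direct effectiveness, without saying which comparison yields the direct effect.

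The arms are set in section 6.1: "i.e. Nyambi health centre in Machinga and Kalembo health centre in Balaka". Machinga is receiving both interventions. Of the comparator the section says "Balaka households do not receive RTS,S vaccination and only receive conventional nets arms". On nets, section 6.2 states: "In Machinga district, PBO nets were distributed, while neighboring Balaka District conventional pyrethroid-treated bed nets were given". Distribution was in November 2018, to whole households, with a target of one net per two people. Section 6.4 has staff record which household members aged 10 or under used which net. Section 6.1 leaves to a later, larger study the "impact of each of these interventions individually and how they interact with each other".

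Section 4 says RTS,S vaccination will be evaluated for its effect on the prevalence of "infection in the vaccinated children and their household members and also on various measures of transmission". It adds that knowledge of the "direct and indirect, population-level benefits of malaria vaccination and PBO nets will be critical when countries decide" on adoption.

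**The concern.** The older children are treated as people who can be affected only through others. That is true of the vaccine, because they are outside its age range, but not of the nets, which reach the whole household. A Nyambi–Kalembo difference in these children would therefore include the direct effect of half the package.

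A result headed indirect effectiveness would be read as spillover, and section 4 invites reading it as spillover from vaccination. The siblings' own PBO nets could produce such a result with no spillover at all, and a district difference could produce or hide one. Phase 1 feeds a Go/No-Go assessment (Table 2) and its results go to the national malaria programme (section 6.6), so the label affects what others will conclude.

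A related gap concerns the target children. Their between-arm contrast is also a combined one, as sections 6.1 and 6.3.2 acknowledge, but section 6.5 still promises direct effectiveness. Whether that has a comparison group depends on whether children who did not receive RTS,S are enrolled in Nyambi, and the text does not settle this.

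**Working it through.** **The plan's own figure.** Section 6.3.2 gives a detectable effectiveness for the combined interventions in children aged 7–18 months: 34% overall, 36% in the high season and 33% in the low season. With 25 clusters of 20 per arm, two-sided 0.05 and 80% power, a design-effect calculation gives 33.2%, 35.5% and 33.0%. The Hayes–Moulton formula gives 33.6%, 34.8% and 33.5%. The stated figures reproduce to about one point. They concern the package in target children; the plan gives no figure for indirect effectiveness.

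**Identification.** On a suitable scale, write the mean sibling outcome in each arm as:

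- Kalembo: baseline
- Nyambi: baseline + own PBO-net effect + community PBO-net effect + RTS,S spillover + district difference

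There are two means and five unknowns (rank 2). Their difference is the sum of the last four terms, and no single term can be recovered. Section 6.2 says both districts have vaccinating and control clusters, but Phase 1 recruits from neither the RTS,S-only nor the PBO-only combination.

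Enrolment samples cannot remove the district term. Recruitment is planned for December 2019 (Table 2), 13 months after the nets, so enrolment is not a pre-intervention baseline.

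**How large the own-net and district terms could be, with vaccine spillover set to zero.** Inputs:

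- sibling risk in Kalembo 31% (section 6.3.2, children up to 10 years);
- cited PBO effect 44% in year one and 33% in year two (section 3.2). Follow-up from January to October 2020, reading Table 2's January 2019 as 2020, falls 14–23 months after distribution, so 33% is the nearer figure;
- 2015 district incidence: for Machinga, "malaria annual incidence was 367 cases/1,000 individuals"; for Balaka, 310 per 1,000;
- ITN use in Machinga: 66.3% of individuals, 80.5% of under-fives (section 6.2).

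Apparent effectiveness is 1 − (Nyambi risk / Kalembo risk):

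| Assumption | Nyambi risk | Apparent effectiveness |
|---|---|---|
| Year-two effect as published | 0.67 × 31% = 20.8% | 33.0% |
| Year-one effect as published | 0.56 × 31% = 17.4% | 44.0% |
| Year-two effect and district ratio 367/310 = 1.184 | 0.67 × 1.184 × 31% = 24.6% | 20.7% |
| Year-two effect, same ratio reversed (310/367 = 0.845) | 0.67 × 0.845 × 31% = 17.5% | 43.4% |

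Scaling the effect by net use instead, and ignoring district, the range runs from 0.663 × 33% = 21.9% to 0.805 × 44% = 35.4%. With 500 siblings per arm (assumed) and the planning intracluster correlation of 0.14, the effective size per arm is 500 / (1 + 19 × 0.14) = 136.6. An own-net effect in that range would then be declared significant in 24% to 55% of studies, although the true indirect effect is zero.

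**Who is enrolled in Nyambi.** The texts side by side:

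- Section 6.4 first identifies households where children have already received RTS,S and PBO nets. It then says age-eligible children will be traced from registers.
- Section 6.1, the criteria in section 6.3 and the household-child paragraph of section 6.4 require only age-eligibility.
- Section 6.5 describes children who do and do not comply with RTS,S.

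On the first reading there is no unvaccinated comparison group within Nyambi; on the others there may be one.

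**The case against.** The strongest reply is that section 6.5 leaves the sibling comparison open, so the net-use data could rescue it: compare Nyambi children not under PBO nets with Kalembo children. This has some force. Splitting Nyambi by net use raises the rank from 2 to 3, and the own-net effect then separates if net use is unconfounded. But section 6.5 does not plan it, net use is self-selected, and both spillovers still merge with the district difference. The causal models in 6.5 are proposed only for total and direct effectiveness.

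Second, section 6.1 defers individual effects and section 6.3.1 calls the household data preliminary. Section 4 also argues partly for the wider programme. All true, but none of it corrects the estimands named in 6.5.

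Third, indirect effectiveness could mean the package, in which case community protection from PBO nets would count. That is a fair reading. The contrast would still contain the child's own net protection and the district difference, so it would not be an indirect effect of the package either.

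Fourth, the illustration has limits, and these stand. The cited 33% and 44% come from a cluster-randomised trial and may include community protection. The district figures are for whole districts and for incidence, not infection. Section 6.2 also reports malaria as 24% of outpatient attendance in Machinga and 29% in Balaka, the opposite ordering, although that share is not a rate. The direction for these two catchments is unknown, which is why both are shown. The 31% base lies outside its own seasonal range of 32–46%, but it cancels from the relative contrasts.

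**Conclusion.** The concern holds. As written, section 6.5 claims an estimand that the two-catchment comparison cannot deliver. The sibling contrast is a between-arm difference for the package, including own net use, and is confounded with district. This conclusion rests only on who received which nets and on there being one catchment per arm; it needs no numerical assumption.

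The size is illustrative. With no vaccine spillover, the contrast could read anywhere from about 21% to 44%. That range assumes that the cited PBO effects transfer to this setting and, for some of the values, that the 2015 district ratio carries over to infection risk or that ITN use stands in for PBO-net use. The target-child contrast has the same attribution limit, and direct vaccine effectiveness has no defined comparison until enrolment in Nyambi is clarified.

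**What to change.** 1. In section 6.5, rename the sibling estimand as the between-arm difference in household members for the RTS,S plus PBO-net package, including own net use. Rename the target-child contrast as the between-arm difference for the combined package. State that Phase 1 cannot attribute either to vaccination or to nets alone and that, with one catchment per arm, both are confounded with district.

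2. Reconcile section 6.4 with sections 6.1, 6.3 and 6.5 on whether children who did not receive RTS,S are enrolled in Nyambi. If they are not, remove direct vaccine effectiveness from 6.5 and keep the baseline description of dose completeness and net use. If they are, define direct effectiveness as a non-randomised comparison within Nyambi and report it with its confidence interval.

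3. If a comparison of Nyambi siblings not using PBO nets with Kalembo siblings is wanted, specify it as exploratory with the limits above.

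The first change is wording only: registers, visits, samples and sample size stay as they are. The second is also a text change, but it records a decision about who is recruited, and the plan gives no power for a comparison within Nyambi. The third uses net data already being collected.
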